2.3 Blinding and Unblinding

Not applicable. This is an open-label study.

2.4 Protocol Amendments

Table 2.4-1 below includes a list of the protocol amendments and administrative letters.

Table 2.4-1: Protocol amendments and administrative letters

Document	Date of Issue	Summary of Change
Revised Protocol 03	27-Jul-2018	Revised Protocol 03 incorporates revisions to allow single agent treatment of nivolumab for on-study participants with non-small cell lung cancer (NSCLC). Only triple-negative breast cancer (TNBC) and pancreatic adenocarcinoma (PAC) participants who are deriving clinical benefit will continue to be treated with the nivolumab plus daratumumab combination therapy. Enrollment of all tumor types is closed, as of 26-May-2018. The enrollment of participants with NSCLC was closed due to the lack of an efficacy signal. The enrollment of participants with TNBC and PAC was previously closed as the study had met enrollment goals in these 2 cohorts. Pharmacokinetic, immunogenic, [REDACTED] will no longer be collected in this study. [REDACTED]
Administrative Letter 05	16-Feb-2018	Included additional available potencies for Daratumumab Solution for Injection to include 400mg potency.
Administrative Letter 04	26-Jan-2018	Clarified the eligibility criteria for the pancreatic adenocarcinoma (PAC) and triple negative breast cancer (TNBC) cohorts
Administrative Letter 03	17-Nov-2017	Clarified the eligibility criteria for the pancreatic adenocarcinoma cohort.
Administrative Letter 02	04-Aug-2017	Clarified protocol requirements for tumor tissue submission at screening and updated Medical Monitor
Revised Protocol 02	14-Jun-2017	Incorporates Amendment 03
Amendment 03	14-Jun-2017	[REDACTED] Adds clarification that prior focal radiation therapy as palliative treatment to a non-index lesion is permitted up to 2 weeks from starting study therapy. Added to the inclusion criteria are permitted time windows prior to start of study therapy for the use of supportive measures to achieve required screening laboratory values. Clarification of inclusion criteria for participants with triple negative breast cancer and pancreatic adenocarcinoma to include, in addition to history of progression or refractory disease, best response of stable disease to prior treatment regimens. Correction to remove height from baseline assessments. Modification in RECIST 1.1 (Appendix 7) to clarify minimum duration of stable disease.

Table 2.4-1: Protocol amendments and administrative letters

Document	Date of Issue	Summary of Change
Administrative Letter 01	03-May-2017	Clarification that the whole blood biomarker sample at screening is not required; the scheduled whole blood collection at Week 1/Day 1 will be used for baseline biomarkers assessments
Revised Protocol 01	18-Apr-2017	Incorporates Amendment 02
Amendment 02	18-Apr-2017	Adds American Society of Clinical Oncologists and College of American Pathologists (ASCO-CAP) guidelines as part of the inclusion criteria definition of HER2 negativity in triple negative breast cancer as requested by the FDA. Revision of creatinine clearance threshold for eligibility, as recommended by the FDA.

3 OBJECTIVES

This section includes only the primary and secondary objectives since these will be analyzed as part of the synoptic clinical study report. The study protocol includes the complete list of study objectives.

3.1 Primary

To establish the tolerability of the combination of nivolumab and daratumumab in participants with advanced or metastatic solid tumors.

3.2 Secondary

- To evaluate the objective response rate (ORR) of nivolumab combined with daratumumab in participants with advanced or metastatic tumors in each cohort.
- To assess progression free survival (PFS) of nivolumab combined with daratumumab in participants with advanced or metastatic tumors in each cohort.
- To characterize the pharmacokinetics of nivolumab and daratumumab in participants with advanced or metastatic tumors.
- To characterize the immunogenicity of nivolumab and daratumumab in participants with advanced or metastatic tumors

4 ENDPOINTS

This section includes only the endpoints that will be analyzed as part of the synoptic clinical study report.

4.1 Efficacy Endpoints

Efficacy endpoints are ORR and median PFS in each cohort in each cohort, based on RECIST 1.1 criteria. In addition, duration of response (DOR), best overall response (BOR) and disease control rate will also be analyzed, which are also described in this section.

4.1.1 Objective Response Rate

Objective Response Rate (ORR) is defined as the number of treated subjects who achieve a best response of complete response (CR) or partial response (PR) based on investigator assessments (using RECIST v1.1 criteria) divided by the number of all treated subjects. Best Overall Response (BOR) is defined as the best response, as determined by Investigator, recorded between the date of first dose and the date of objectively documented progression per RECIST v1.1 criteria or the date of subsequent therapy, whichever occurs first. For subjects without documented progression or subsequent therapy, all available response designations will contribute to the BOR determination. Subsequent therapy includes any therapy (systemic cancer therapy, surgery, radiotherapy).

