**Table 9.1.1-2: Schedule of Spiral CT/MRI Tumor Assessments for advanced and Metastatic Cohorts**

Tumor Assessment Frequency	Assessment Window
Tumor assessment at screening (within 28 days of first dose), and then every 6 weeks thereafter up to 24 weeks	± 1 week
Tumor assessment at week 24 and beyond will be every 12 weeks until PD.	± 2 weeks

For the 3 advanced metastatic tumor cohorts a baseline tumor assessments will be performed within 28 days prior to the start of treatment. Participants will then be evaluated for tumor response beginning 6 weeks from the date of first dose (± 1 week.), then every 6 weeks (± 1 week.) thereafter up to 24 weeks, then it will be every 12 weeks (+/- 2 weeks) until disease progression is documented, regardless of early treatment discontinuation due to reasons other than PD, or subsequent therapy is initiated (whichever occurs first).

Confirmation Scans are required as follows:

- Verification of Response: Confirmation of PR and/or CR is required after at least 4 weeks to ensure responses identified are not the result of measurement error.
- Verification of Progression: When not clinically burdensome to the participant, confirmation of PD is required after at least 4 weeks to ensure responses identified are not the result of measurement error.

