##### 4.1.1 **Missing assessments and not evaluable designation**

When no imaging/measurement is done at all at a particular time point, the subject is **not evaluable (NE)** at that time point. If only a subset of lesion measurements are made at an assessment, the case is also considered NE at that time point, unless a convincing argument can be made that the contribution of the individual missing lesion(s) would not have changed the assigned time point response.

- Confirmation of PR and CR is required after at least 4 weeks to ensure responses identified are not the result of measurement error.

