LIST OF FIGURES

Figure 1.1-1: Study Design Schematic 6

Schedule of Analyses:

Interim analyses for futility were planned, separately for TNBC, NSCLC and PAC. Analyses were to be based on the first 20 participants of each cohort, after 4 months on treatment. The database lock (DBL) for the PAC interim was planned for Q2 2018; and for TNBC was anticipated for Q3 2018.

Under the circumstance that data of some tumor types mature faster than others or a strong signal was observed in some tumor types, additional interim analyses may have been performed prior to the completion of the study in order to facilitate program decisions such as expanding the current study or starting phase 3 development and to support presentations or publications.

Final analyses of each fully-accrued cohort was to be conducted, separately for each cohort.

On 13-June-2018, investigators were informed that Protocol CA209-9GW would be amended to allow single agent treatment of nivolumab for on-study participants with non-small cell lung cancer (NSCLC). In addition, only triple-negative breast cancer (TNBC) and pancreatic adenocarcinoma (PAC) participants who are deriving clinical benefit would continue to be treated with the nivolumab plus daratumumab combination therapy.

The enrollment of participants with NSCLC was closed due to the lack of an efficacy signal. This decision was not related to any serious adverse events associated with the use of nivolumab in combination with daratumumab. The enrollment of participants with TNBC and PAC was previously closed as the study had met enrollment goals in these 2 cohorts.

At that time, the protocol defined interim analysis was done after 20 patients treated for each cohort for both TNBC and PAC. The combination was discontinued before 20 patients were treated in the NSCLC cohort, thus the protocol defined interim analysis was not performed.

Following the decision of BMS to stop enrollment, only a final close out analysis will be performed at the end of the study. This statistical analysis plan describes these.

[figure not shown]

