4.1.3 Duration of Response

Duration of Response (DOR) is defined as the time between the date of first documented response (CR or PR) to the date of the first documented tumor progression as determined by Investigator (per RECIST v1.1 criteria), or death due to any cause, whichever occurs first. Subjects who start subsequent therapy without a prior reported progression will be censored at the last evaluable tumor assessments prior to initiation of the subsequent anticancer therapy. Subsequent therapy includes any therapy (systemic cancer therapy, surgery, radiotherapy). Subjects who die without a reported prior progression will be considered to have progressed on the date of their death. For subjects who neither progress nor die, DOR will be censored on the date of their last evaluable tumor assessment. DOR will be evaluated for responders (CR or PR) only.

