6.3 Populations for Analyses

- All Enrolled subjects: All subjects who signed the informed consent form and obtained a subject number.
- All Treated subjects: All enrolled subjects who received at least one dose of any study treatment. This will be both efficacy and safety population.
- Subjects Entered Follow-up: All subjects who entered the follow-up period as specified in subject status CRF pages.
- All Treated Subjects with Objective Response: All treated subjects with response of CR or PR per RECIST v1.1 per Investigator.

Unless otherwise specified, the efficacy and safety analyses will include all treated subjects.

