7.4.1 Analysis of Objective Response Rate and Disease Control Rate

One of the objectives of the study is to estimate the ORR per Investigator among all treated subjects.

The number and percentage of subjects in each category of BOR per Investigator (complete response [CR], partial response [PR], stable disease [SD], progressive disease [PD], or unable to determine [UTD]) will be presented. Estimates of response rate and disease control rate, along with its exact two-sided 95% CI by Clopper and Pearson³ will be presented.

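### SAP 4.1.1 derives best overall response without the confirmation of CR/PR that the protocol requires, so an unconfirmed response can count in ORR and DOR

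*SAP*

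**What the plan says.** SAP 4.1.1 defines ORR as treated subjects with a best response of CR or PR by investigator, under RECIST v1.1, over all treated subjects. It then gives the operative rule: "Best Overall Response (BOR) is defined as the best response, as determined by Investigator, recorded between the date of first dose" and the earlier of documented progression or subsequent therapy. For subjects with neither, it adds that "all available response designations will contribute to the BOR determination".

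The later SAP sections use the same responders:

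- 4.1.3: "DOR will be evaluated for responders (CR or PR) only".
- 6.3, the objective-response population: "All treated subjects with response of CR or PR per RECIST v1.1 per Investigator".
- 7.4.1, the response table: "The number and percentage of subjects in each category of BOR per Investigator", with Clopper-Pearson intervals for the response and disease control rates.

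None of these mentions confirmation.

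The protocol does. Under Table 9.1.1-2 in section 9.1.1: "Confirmation of PR and/or CR is required after at least 4 weeks to ensure responses identified are not the result of measurement error". Appendix 7 section 4.1.1 repeats it: "Confirmation of PR and CR is required after at least 4 weeks to ensure responses identified are not the result of measurement error", and so does its section 4.1.2. Appendix 7 section 4.2 builds confirmation into the definition of best response, and its Table 2 is the version for trials in which confirmation is required. The Synopsis and Table 4.-1 tie ORR, DOR and BOR to Appendix 7.

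**The concern.** The SAP is the text that will be programmed for the close-out report. Two competent programmers could produce different ORRs from it: one would take the best designation recorded in the window, the other would apply Appendix 7 Table 2. The protocol says why confirmation is needed, namely to guard against measurement error. There is also no independent check on the investigator's reading, because Revised Protocol 03 removed blinded independent review.

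At stake are the two reported measures of activity, ORR and DOR. ORR also has stated levels of clinical interest: above 10% for TNBC and PAC, and above 20% for NSCLC.

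**Working it through.** **1. The two rules applied to the same subject.** First scan in the pair shows PR; the second column is the next time point.

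| First | Next | SAP 4.1.1, read literally | Protocol Appendix 7 Table 2 |
|---|---|---|---|
| PR | PR | PR | PR |
| PR | SD | PR | SD |
| PR | PD | PR | SD if the minimum SD duration is met, otherwise PD |
| PR | NE | PR | SD if the minimum SD duration is met, otherwise NE |

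The rules differ in three of the four rows, always in the same direction. Every confirmed responder also has a recorded CR or PR, so over the same window literal ORR ≥ confirmed ORR.

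**2. The plan's own intervals.** Clopper-Pearson limits for x of n are the 2.5% quantile of Beta(x, n−x+1) and the 97.5% quantile of Beta(x+1, n−x). For n = 40:

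- 4/40 gives 2.8% to 23.7% and 8/40 gives 9.1% to 35.6%, both as in SAP Table 5-1.
- 9/40 has a lower limit of 10.8%, so SAP section 5 is right that 9 is the smallest count whose interval excludes 10%.

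**3. Effect of one unconfirmed response.**

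- Cohort of 40: 1/40 = 2.5 percentage points.
- NSCLC: according to the SAP's Schedule of Analyses, "The combination was discontinued before 20 patients were treated in the NSCLC cohort". With at most 19 treated, one subject is at least 1/19 = 5.3 points.
- Starting from the first column of Table 5-1, 4/40 = 10.0% (95% CI 2.8 to 23.7) becomes 5/40 = 12.5% (95% CI 4.2 to 26.8).
- One subject can also cross the section 5 threshold: 8/40 has a lower limit of 9.1%, 9/40 of 10.8%.

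**4. What does and does not move in DOR and DCR.**

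- The DOR start date is the same under both readings. SAP 4.1.3 and Appendix 7 section 4.3 both start at the first CR or PR. Only membership of the set changes.
- DCR does not change for scans done within their windows. The earliest in-window first scan is at (6 − 1) × 7 = 35 days, which equals the 35-day minimum for SD in footnote b of Table 2. An unconfirmed PR therefore becomes SD and still counts as disease control.

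**5. Can the existing scans confirm a response?** Shortest gaps between consecutive in-window scans, from the windows in protocol 9.1.1:

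- Weeks 6 to 12: (12 − 1) − (6 + 1) = 4 weeks; the same for 12 to 18 and 18 to 24.
- Weeks 24 to 36: (36 − 2) − (24 + 1) = 9 weeks.
- Weeks 36 to 48: (48 − 2) − (36 + 2) = 8 weeks.

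These take week 24 at ±1 week, as the text below Table 9.1.1-2 does. If the table's second row is read as giving week 24 itself ±2 weeks, the shortest gap from week 18 is (24 − 2) − (18 + 1) = 3 weeks, and the following scan would have to confirm.

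**The case against.** The strongest reply is that the SAP does not waive confirmation; it is only silent. It defines ORR under RECIST v1.1, and in this trial RECIST 1.1 is set out in Appendix 7, where best response takes confirmation into account. The sentence on all available designations fits a confirmed derivation too, since Table 2 needs pairs of time points. This stands in part: the confirmed reading is open. But the SAP's endpoint sections never point to Appendix 7 or Table 2, while their explicit rule is the best response recorded. A reader who follows that rule gets a different answer.

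A second reply is that protocol 10.3.1 defines BOR in almost the same way and is equally silent. That is true. Section 10.3, however, introduces it as a summary and leaves detail to the SAP, and the same protocol ties the endpoints to Appendix 7. Aligning 10.3.1 would do no harm but is not needed.

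A third reply is that little depends on this: the primary endpoint is safety, SAP 7.4 reports no p-values, enrollment is closed, and the two intervals for 4/40 and 5/40 support much the same conclusion. This stands as a limit on importance. Also fair is that Table 2 covers only two time points and does not settle sequences such as PR, SD, PR or PR, NE, PR.

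**Conclusion.** The concern holds. As written, the SAP rule can admit responders whom the protocol's rule excludes, and none of its sections corrects this. The error can run only one way for ORR: zero or upward, by 2.5 points per subject in a cohort of 40 and by at least 5.3 points per subject in NSCLC. The composition of the DOR set changes too. DCR for in-window scans and the DOR start date do not.

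This assumes 40 treated in TNBC and in PAC (the target; the final treated counts are not given) and the same BOR window under both rules, which SAP 4.1.1 and protocol 10.3.1 share. The documents give no rate of non-confirmation, so the one-subject examples are illustrations and the total effect cannot be stated. The point affects descriptive secondary results only, but it should be settled before the close-out analysis is programmed.

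**What to change.** In SAP 4.1.1, state that a best response of CR or PR counts only when confirmed at least 4 weeks later according to protocol Appendix 7 Table 2, within the existing BOR window, and that an unconfirmed CR or PR is reclassified as that table directs. Carry the word confirmed into the responder sets of 4.1.3 and 6.3, leaving the DOR start at the first documented response. The same clause should say how sequences with an intervening SD or NE are handled, because Table 2 does not. An unconfirmed ORR, labelled as such, may be added as a supportive line.

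The cost is this SAP wording. It needs no protocol amendment and no scans beyond those already required, and it changes no sample size or power figure. The downside is that the reported ORR may be slightly lower, because a response first seen at a subject's last scan cannot be confirmed.

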4.1.2 Disease Control Rate

Disease Control Rate (DCR) is defined as the number of treated subjects who achieve a best response of complete response (CR), partial response (PR) or stable disease (SD) based on investigator assessments (using RECIST v1.1 criteria) divided by the number of all treated subjects.

4.1.3 Duration of Response

Duration of Response (DOR) is defined as the time between the date of first documented response (CR or PR) to the date of the first documented tumor progression as determined by Investigator (per RECIST v1.1 criteria), or death due to any cause, whichever occurs first. Subjects who start subsequent therapy without a prior reported progression will be censored at the last evaluable tumor assessments prior to initiation of the subsequent anticancer therapy. Subsequent therapy includes any therapy (systemic cancer therapy, surgery, radiotherapy). Subjects who die without a reported prior progression will be considered to have progressed on the date of their death. For subjects who neither progress nor die, DOR will be censored on the date of their last evaluable tumor assessment. DOR will be evaluated for responders (CR or PR) only.

4.1.4 Progression-Free Survival

PFS rate at time T is defined as the probability that a subject has not progressed and is alive at time T following start of treatment. PFS rates at fixed time points (e.g. 6 months, depending on the minimum follow-up) are defined as the probability that a subject has not progressed and is alive at time T following start treatment date.

Disease assessment with CT and/or MRI, as appropriate, will be performed at baseline and every 6 weeks up to 24 weeks, and every 12 weeks thereafter until PD, the completion of follow-up, initiation of new therapy, or participant withdraw from the study. Tumor responses will be assessed by the investigator as defined by RECIST v1.1.

PFS is defined as the time between the date of treatment start day and the date of first documented tumor progression, based on Investigator assessments (per RECIST v1.1 criteria), or death due to any cause, whichever occurs first.

Subjects who die without a reported progression will be considered to have progressed on the date of their death. The following censoring rules will be applied for the primary definition of PFS:

- Subjects who did not progress or die will be censored on the date of their last evaluable tumor assessment.
- Subjects who did not have any on study tumor assessments and did not die will be censored on their first dosing date.
- Subjects who receive subsequent anti-cancer therapy prior to documented progression will be censored at the date of the last evaluable tumor assessment conducted on or prior to the date of initiation of the subsequent anti-cancer therapy.
- Subjects who did not have a documented progression and received subsequent anti-cancer therapy will be censored at the date of the last evaluable tumor assessment conducted on or prior to the initiation of the subsequent anti-cancer therapy.
- Subsequent therapy includes any therapy (systemic cancer therapy, surgery, radiotherapy).

Censoring rules for the primary definition of PFS are presented in Table 4.1.4-1.

Table 4.1.4-1: Censoring Scheme used in Primary Definition of PFS

Situation	Date of Progression or Censoring	Outcome
No baseline tumor assessments*	Date of first dose	Censored
No on study tumor assessments and no death*	Date of first dose	Censored
Subsequent anti-cancer therapy started without death or progression per RECIST v1.1 reported prior or on the same day	Date of last evaluable tumor assessment prior to or on the date of initiation of the subsequent anti-cancer therapy	Censored
Documented progression per RECIST v1.1 and no new anti-cancer started before	Date of the first documented progression per RECIST v1.1 (excludes clinical progression)	Progressed
No progression and no death, and no new anti-cancer therapy started	Date of last evaluable tumor assessment	Censored
Death without progression per RECIST v1.1 and no new anti-cancer started before	Date of death	Progressed

* Tumor assessments and death if any, occurring after start of subsequent anti-cancer therapy are not considered.

4.2 Safety endpoints

The assessment of safety will be based on the incidence of adverse events (AEs), serious adverse events (SAEs), adverse events leading to discontinuation, and deaths. In addition, specific laboratory abnormalities will be summarized and listed.

